3.0 Study Design

This is a double blind, parallel group, placebo controlled feasibility study (see figure 1) with an enrollment target of 60 patients (30 per arm). All subjects that meet inclusion criteria as an outpatient, following a 1 month observation, will be randomized to receive an oral prophylactic dose factor Xa inhibitor (Apixaban 2.5mg po bid) or placebo for 6 months. Subjects will return for a 30 day (+/- 5 days) follow-up visit after the End of Treatment (EOT) visit. Initial randomization will occur by computerized randomization technique by the investigational drug services (IDS) at Duke University Medical Center.

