principal investigator. Pain scores during hospitalization and for the subsequent 1 week will be recorded and used for secondary analysis of daily pain scores during crisis.

Patients who during the course of the study have laboratory findings which reveal creatinine ≥ 1.5 mg/dL AND weight ≤ 60 kg; platelets $< 100 \times 10^9/L$; or develop AST or ALT > 3 times normal, will have study drug stopped and will be terminated from the study.

Patients on hydroxyurea will be included in the study and sub-analysis will be performed to control for potential differences. All patients despite treatment with hydroxyurea will need to meet inclusion criteria of having clinically significant pain which requires > 2 acute care visits.

4.2 Data and Statistical Analysis Aim 1

We power the study to test whether there is a significantly larger reduction in pain after administration of a daily prophylactic anticoagulation dose as compared to administration of a placebo. A total of 60 patients will be randomly assigned to each drug arm. The primary endpoint is the mean pain score per patient over each of four time periods. The design has two sources of variation: the variation between the patients receiving the same drug and the variation due to the interaction of time by the patients within drug arm. It is of interest to test whether the change in the pain score over the four time periods differs between the prophylactic anticoagulation dose arm and the placebo arm. From the literature the standard deviation of the mean pain score per patient is 1.5. Assume the true mean pain scores over the four time periods for the placebo and prophylactic anticoagulation dose arms are 3.9, 3.9, 3.9, 3.9 and 3.9, 3.12, 3.12, 3.12, respectively. Then, a total of 60 patients randomized equally to each drug arm will detect the difference in the change between the two arms in the mean pain scores over time, as specified by the preceding mean pain scores, with a power of at least 0.836 for a one-sided 0.05 test. Anticipating that 20% (10 patients) may have incomplete data (less than 75% of daily pain scores recorded or missing more than one dose of study drug per week), may be lost to follow up, or may drop out; we have also found a power of at least 78.4% for 50 patients.

We expect two positive effects from prophylactic doses of apixaban on the patient reported outcomes:

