- PROs assessing fatigue, physical function, and pain impact will improve in patients administered daily prophylactic dose apixaban compared to placebo.*
- We believe that there will be a significant correlation between PROs and pain scores.*

Statistical Analysis

The primary outcome of interest is to test the effect on the mean daily pain score due to the arm by time interaction. Secondary outcome will include comparison of daily pain scores while hospitalized between treatment arms and the number of hospitalizations during each treatment period.

Impact of Daily Prophylaxis Dose Anticoagulation with a Factor Xa Inhibitor (Apixaban) in Patients with Sickle Cell Disease

[figure not shown]
All analyses will be performed using SAS version 9 or greater (SAS Institute Inc., Cary, NC). Data will be analyzed using descriptive statistics including mean and standard deviation. Comparisons are to be performed using SAS's PROC GLM with a model that accounts for all fixed and random effects in the design.

5.0 Specific Aim 2: Determine the effect of prophylactic dose anticoagulation on markers of thrombin generation during outpatient steady state as well as inpatient VOC.

As described in section 3.0, we will perform a double blind, parallel group, placebo controlled feasibility study with an enrollment target of 60 patients (30 per arm).

5.1 Study Procedures Aim 2

As described earlier (Figure 1), patients begin a 1 month observation following randomization. Patients will have blood drawn on enrollment and when they return in 1 month (+/- 5 days) to begin study drug. Subsequent blood draws performed at 2 month intervals while on study drug. Blood draws will occur between 2 and 4 hours from previous dose taken and ± 5 days regardless of hospitalization. Patients will be called monthly between in person visits to assess for AE/SAE and to reinforce the importance of medication compliance. Graded incentives may be given monthly to encourage patients to continue on study and return for follow up blood draws.

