5.2 Data and Statistical Analysis

Sample Size

The same design used in Aim 1 applies to Aim 2. We analyze the change in thrombin generation from enrollment to 2 months following initiation of study drug. We hypothesize that the anticoagulation drug will

Impact of Daily Prophylaxis Dose Anticoagulation with a Factor Xa Inhibitor (Apixaban) in Patients with Sickle Cell Disease

cause a decrease in thrombin generation from baseline to two months. From the literature the standard deviation of the D-dimer measure per patient is 500. With a total of 60 patients randomized equally to each drug sequence, and conservatively assuming no correlation between D-dimer values from baseline to 2 months on the same patient, we achieve a power of 0.863 to detect a mean D-dimer difference in the change from baseline to 2 months between the placebo and the daily prophylactic anticoagulation dose groups of 250 mg/l $\{= [(1000-750) - (1000-1000)] \text{ mg/l}\}$ for a one-sided 0.05 test.

No studies to date have evaluated the influence of anticoagulants on thrombin generation as measured by CAT, therefore sample size and expected differences are calculated based on available studies examining D-dimer.

Statistical Analysis

For our primary outcome, we will compare mean changes in thrombin generation (D-dimer, TAT and phases of CAT) for patients treated with prophylactic dose anticoagulation and placebo. Secondary outcomes will include correlation of hypercoagulable and inflammatory markers to clinical outcomes (such as pain, hospitalization, and number of acute care visits).

In addition, we expect that 50% of the patients to be hospitalized and continue their medication (placebo or drug) as assigned at randomization. For these patients, thrombin generation D-dimer measures will be collected at admission, 3 days and 5 days. Therefore, as a secondary aim, for these hospitalized patients we will analyze the difference between the placebo and drug groups in the change over time in the mean D-dimer values.

Planned Analysis of Primary Endpoint

Following the enrollment of the 60 patients, and completion of the 7 month study period for each patient, all data will be subsequently analysed with the assistance of the Duke Translational Medical Institute. [name] is our lead statistician who will continue to provide statistical support and analysis through this study.

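### The Aim 2 power of 0.863 does not follow from its stated inputs: 30 patients per arm at zero correlation gives about 0.39

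*Combined protocol and SAP*

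**What the plan says.** Section 5.2 (Sample Size) says that Aim 2 uses the Aim 1 design and analyses the change in thrombin generation from enrollment to 2 months on study drug. It gives the variability: "From the literature the standard deviation of the D-dimer measure per patient is 500". It describes the sample: "With a total of 60 patients randomized equally to each drug sequence". It then states the result: "conservatively assuming no correlation between D-dimer values from baseline to 2 months on the same patient, we achieve a power of 0.863", for a difference in change of 250 mg/l (1000 to 750 on drug, 1000 to 1000 on placebo) and a one-sided 0.05 test.

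The design is fixed elsewhere. Section 3.0 gives an "enrollment target of 60 patients (30 per arm"), and Section 5.0 repeats it for Aim 2: "we will perform a double blind, parallel group, placebo controlled feasibility study with an enrollment target of 60 patients (30 per arm").

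The standing of the comparison is set in Section 5.2 (Statistical Analysis): "For our primary outcome, we will compare mean changes in thrombin generation (D-dimer, TAT and phases of CAT") between apixaban and placebo. The same section says that, because no CAT data were available, sample size and expected differences rest on D-dimer.

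**The concern.** Every input needed to recompute the power is in the plan, and the stated figure is more than twice what those inputs give.

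Two phrases suggest that the number may come from another layout. Section 5.2 speaks of drug sequences, which is crossover language in a parallel-group trial. Section 4.2 says: "A total of 60 patients will be randomly assigned to each drug arm", which read literally is 60 per arm. Neither settles where 0.863 came from, and the finding does not depend on it.

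What is at stake is how the Aim 2 result is read. If D-dimer shows no difference, a stated power of 0.863 makes that look informative. At 0.39, a null result is the more likely outcome even if the hypothesised 250 mg/l reduction is real.

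**Working it through.** **Inputs**

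- SD of one D-dimer measurement: 500 (Section 5.2)
- Correlation r between baseline and 2 months: 0 (Section 5.2)
- Between-arm difference in change: 250 mg/l (Section 5.2)
- Test: one-sided 0.05, critical value 1.645 (Section 5.2)
- Patients: 30 per arm, parallel groups (Sections 3.0 and 5.0)

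**Attempt to reproduce 0.863 from these inputs**

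1. SD of change = 500 × √(2(1 − r)) = 500 × √2 = 707.1.
2. SE of the between-arm difference = 707.1 × √(2/30) = 182.6.
3. Power = Φ(250/182.6 − 1.645) = Φ(1.369 − 1.645) = 0.391.

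The noncentral t distribution with 58 df gives 0.385, and a simulation of 100,000 trials gives 0.384. The plan's 0.863 is not reproduced. The gap is about 47 percentage points.

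**What 0.863 requires**

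Power of 0.863 needs 250/SE = 1.645 + 1.094 = 2.739, so SE = 91.3. That is half of 182.6. At the stated inputs, the difference detectable with power 0.863 is 2.739 × 182.6 = 500 mg/l, twice the planned effect. Keeping 250 mg/l would take about 121 patients per arm.

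**Other readings**

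| Reading | SE | Power, normal (t) |
|---|---|---|
| 30 per arm, change score, r = 0 (as stated) | 707.1 × √(2/30) = 182.6 | 0.391 (0.385) |
| 30 per arm, 500 taken as the SD of the change | 500 × √(2/30) = 129.1 | 0.615 (0.606) |
| 60 per arm, change score, r = 0 | 707.1 × √(2/60) = 129.1 | 0.615 (0.611) |
| 60 per arm, SD 500 | 500 × √(2/60) = 91.3 | 0.863 (0.86) |
| Within-patient difference in 60 patients, r = 0 | 707.1/√60 = 91.3 | 0.863 (0.856) |
| 30 per arm, change score, r = 0.75 | 353.6 × √(2/30) = 91.3 | 0.863 (0.856) |

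The last three rows reach 0.863, and each contradicts the stated sample size, design or correlation.

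**Range over the correlation**

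The plan gives no correlation other than zero, so 0.5 and 0.75 are assumptions. The 25-per-arm column takes the 50 patients of Section 4.2 ("we have also found a power of at least 78.4% for 50 patients"). Section 5.2 states no attrition for Aim 2, so that column is illustrative. Power is t-based, for the change score.

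| Assumed r | 30 per arm | 25 per arm |
|---|---|---|
| 0 | 0.39 | 0.34 |
| 0.5 | 0.61 | 0.54 |
| 0.75 | 0.86 | 0.79 |

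**The case against.** - **Zero correlation is a cautious assumption.** Repeated measurements on one patient are likely to be positively correlated, so real power may well exceed 0.39. That stands. But 0.863 is claimed at zero correlation, so the caution is supposed to be inside the figure already. Reaching 0.863 with 30 per arm takes a correlation of about 0.75, which the plan neither states nor supports.
- **Pain is the lead endpoint of a feasibility study.** Section 4.2 justifies the same 60 patients by a separate pain calculation, and the planned analysis in Section 5.2 puts pain first and thrombin generation second. This is fair: the error does not undo the trial's overall size. Aim 2 nevertheless has its own sample-size paragraph and a comparison it calls primary, so its power must be correct.
- **The wrong number may be an input.** The documents do not show whether the power, the correlation, the meaning of the SD or the number per arm is at fault. That also stands, so 0.39 is the right replacement only while the stated inputs stand.
- **60 per arm can give 0.863 at zero correlation.** It does for a final-value or baseline-adjusted comparison, where the relevant SD is 500. But Section 5.2 specifies a change score and 60 patients in total. With 30 per arm, those analyses give only about 0.61.
- **Aim 1 attrition does not carry over directly.** Section 4.2 partly counts incomplete pain logs, which do not remove a D-dimer sample. This is why the 25-per-arm figures are only illustrative.

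**Conclusion.** The stated power is wrong as written. With 30 per arm, SD 500 per measurement, zero correlation, a 250 mg/l difference in change and a one-sided 0.05 test, power is 0.39 (t-based 0.385), not 0.863. No reading examined that keeps both 30 per arm and zero correlation exceeds about 0.61.

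This conclusion uses only inputs printed in the plan. The actual power depends on a correlation the documents do not supply, and the origin of 0.863 remains unknown. Neither affects the finding that the figure does not follow from its inputs. It must be corrected because it bears on an outcome the plan names as primary for Aim 2.

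**What to change.** 1. In Section 5.2, replace 0.863 with about 0.39 for 30 per arm at the stated zero correlation. Add the range: 0.61 at a correlation of 0.5 and 0.86 at 0.75 with complete data; 0.34, 0.54 and 0.79 at correlations of 0, 0.5 and 0.75 with 25 per arm. If the sponsor finds that an input was misstated, correct that input with its source and recompute. The sample size is unchanged.
2. In the same paragraph, refer to arms instead of sequences.
3. Optional, and not needed to correct the power statement: analyse 2-month D-dimer by ANCOVA, adjusting for the mean of the two pre-drug draws already scheduled in Section 5.1 (enrollment and Month 1). Assuming equal correlation r among the three draws, the residual variance is 500² × (1 − 2r²/(1 + r)). At r = 0, 0.5 and 0.75, t-based power is about 0.61, 0.76 and 0.94 with 30 per arm, and 0.54, 0.69 and 0.90 with 25 per arm. This changes the planned estimator and the definition of baseline, so it must be pre-specified.

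Items 1 and 2 are wording only, with no added patients, visits or samples. Their one cost is a less favourable stated power. Item 3 uses existing draws but changes the analysis.

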Platelet poor plasma will be separated and stored to allow batch testing for hypercoagulable markers and markers of inflammation. Markers of thrombin generation will include D-dimer, thrombin-antithrombin (TAT) complex, and CAT. Both D-dimer and TAT will be performed using enzyme-linked immunosorbent assay (ELISA). CAT will be performed using the Fluoroskan Ascent plate reader (TCoag) and phases to be analyzed include lag phase, slope, peak and endogenous thrombin potential. Markers of inflammation will also be measured at each of these time points (IL-6 and sVCAM) which are performed by ELISA.

Patients admitted to the hospital will continue their study drug or placebo unless deemed medically inappropriate by admitting physician. Patients upon discharge are to resume study drug per supervision of study principal investigator. Blood will be drawn for secondary analysis for hypercoaguability on any inpatient hospitalizations on day 1, 3 and 5 but will not be included in primary analysis.

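### Aim 2 gives six measures the primary label with no lead marker, testing order, success rule or multiplicity adjustment, and only D-dimer is sized

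*Combined protocol and SAP*

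**What the plan says.** The Statistical Analysis paragraph of section 5.2 says of the Aim 2 primary outcome: "we will compare mean changes in thrombin generation (D-dimer, TAT and phases of CAT", comparing the apixaban and placebo arms. Section 5.1 adds, for CAT, that "phases to be analyzed include lag phase, slope, peak and endogenous thrombin potential". With D-dimer and TAT, that makes six measures.

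The Sample Size paragraph of section 5.2 deals with one of the six: "we achieve a power of 0.863 to detect a mean D-dimer difference in the change from baseline to 2 months", "for a one-sided 0.05 test". It explains that CAT data under anticoagulation were lacking, so "sample size and expected differences are calculated based on available studies examining D-dimer". No level, direction of test or effect size is given for TAT or for any CAT phase.

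Under Planned Analysis of Primary Endpoint, at the end of section 5.2, the primary analysis is of daily pain scores. The change in thrombin generation from enrollment to two months is added after it, and secondary analyses follow in a separate paragraph. Section 4.2 likewise names pain as the primary outcome of Aim 1. Sections 3.0 and 5.0 call the trial a feasibility study.

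The document contains no ranking of the six measures, no composite, no statement of how many must be positive, and no adjustment.

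**The concern.** A primary outcome should tell the reader in advance which result would count as success. Here it does not. Success could mean a positive D-dimer result, a positive result on any of the six, on most of them, or on all of them. These rules have very different error rates. If all six must be positive, the false-positive rate cannot exceed the 5% of a single test. If any one is enough, it can be several times that.

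The choice could therefore be made after the results are known. A favourable finding on one CAT phase, with D-dimer and TAT flat, could be reported as the Aim 2 primary result, although the 5% level and the power statement were set out for D-dimer only.

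**Working it through.** **Number of measures.** D-dimer (1) + TAT (1) + lag phase, slope, peak and endogenous thrombin potential (4) = 6. All are compared at one contrast, enrollment to two months on drug, so there is no further multiplication over visits.

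**The plan's own figure.** Section 5.2 gives a power of 0.863. Its inputs are: "the standard deviation of the D-dimer measure per patient is 500"; "conservatively assuming no correlation between D-dimer values from baseline to 2 months on the same patient"; a difference in change of 250 mg/l; 60 patients in total, 30 per arm; one-sided 0.05 (z = 1.645). Power is Φ(difference / SE − 1.645), with SE = SD × √(2/n per arm).

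- SD of the change at zero correlation: 500 × √2 = 707.1.
- SE at 30 per arm: 707.1 × √(2/30) = 182.6.
- Power: Φ(250/182.6 − 1.645) = Φ(−0.276) = 0.391, or 0.385 with the noncentral t.
- With SD 500 in place of 707, at 30 per arm: SE = 129.1 and power = 0.615.
- With SD 500 and 60 per arm: SE = 91.3 and power = Φ(2.739 − 1.645) = 0.863.
- A paired crossover of 60 patients with a difference SD of 707 has the same SE, 707.1/√60 = 91.3, and the same power.

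So 0.863 is not reproduced from the stated parallel design. Of the variants tried, only 60 per arm with SD 500, or the equivalent crossover calculation, returns it. The sample-size sentence also speaks of drug sequences rather than arms, which suggests text carried over from a crossover design.

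**False-positive rate under an any-one-of-six rule.** This assumes each measure is tested at one-sided 0.05. The plan states that level for D-dimer; for the other five it is an assumption.

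- Independent tests: 1 − 0.95^6 = 1 − 0.735 = 0.265.
- Upper bound under any dependence: 6 × 0.05 = 0.30.
- Correlated tests: simulated as six one-sided z-tests, 1,000,000 draws, counting draws in which the largest exceeds 1.645. The documents give no correlations, so all of these are assumed.

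| Assumed correlation | False-positive rate |
|---|---|
| 0.3, all pairs | 22.0% |
| 0.5, all pairs | 18.6% |
| 0.7, all pairs | 14.8% |
| 0.9, all pairs | 10.0% |
| 0.8 among CAT phases, 0.3 for other pairs | 17.5% |

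**Splitting alpha instead.** Bonferroni gives 0.05/6 = 0.0083 per test and a familywise rate of 4.9% under independence. D-dimer power would then be about 0.15 with the stated inputs, and about 0.63 with the inputs that return 0.863.

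**The case against.** The strongest defence is that the label is local to the aim. Pain is the trial's primary analysis, the marker comparison is appended to it, and this is a feasibility study with laboratory markers. On that view, 'primary' in section 5.2 means only the main analysis of a biomarker aim. This stands as far as the trial-level hierarchy goes. It does not remove the gap: section 5.2 still states a directional hypothesis, a level and a power, calls the marker comparison primary, and places it ahead of the secondary analyses.

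A second defence is that D-dimer is the lead marker by implication, since it is the one sized. The text does not say so. It gives lack of CAT data as the reason for sizing on D-dimer, and the Study Rationale presents CAT as the assay for following thrombin generation on treatment.

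Some stronger readings are tempting but unsupported:

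- A reader might infer that the plan lets any single marker declare success at one-sided 0.05. It says neither that one suffices nor that TAT and CAT are tested at that level. The success rule is unspecified.
- A reader might take 26% as the error rate or as its ceiling. It is the independence value. The strict bound is 30%, and because four measures come from one CAT curve the rate is probably below 26%.
- A reader might add the Aim 1 pain test to the family. The plan keeps the two aims apart and never pools them into one claim.

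**Conclusion.** The omission is plain on the page: six measures carry the Aim 2 primary label, one is sized, and nothing says how they are to be judged together. The size of the risk is conditional. Under an any-one rule at one-sided 0.05 for each measure, it is about 26% with independent tests and about 10% to 22% for assumed common correlations of 0.9 to 0.3. Every scenario calculated is at least double the 5% used for sizing, so the conclusion does not depend on independence. It does depend on the any-one rule, which the plan leaves open but does not state. The point affects how an Aim 2 result can be claimed. It does not bear on the pain analysis.

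**What to change.** In section 5.2, name one Aim 2 primary comparison: the between-arm difference in D-dimer change from enrollment to two months on study drug. Study drug is dispensed at Month 1 and blood is drawn at Month 3, so the existing schedule already provides the sample. List TAT and the four CAT phases as secondary, with Holm-adjusted p-values or a plain statement that their p-values are exploratory. State that daily pain is the trial-level primary. Make the change before unblinding.

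This changes wording only, with no effect on data collection, but two consequences should be disclosed. TAT or CAT alone could no longer carry the Aim 2 primary claim. And Aim 2 would rest on a comparison whose power under the plan's own inputs is about 0.39, so the 0.863 should be restated, or the inputs that produce it justified for a 30-per-arm parallel design.

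If the investigators regard another marker as the lead, naming that one, or fixing a testing order, would also close the gap. D-dimer has the advantage of matching the only sample-size statement in the plan.

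### The in-hospital D-dimer contrast named in Section 5.2 uses an on-treatment admission value as its baseline, so it can miss or reverse a sustained drug effect

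*Combined protocol and SAP*

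**What the plan says.** The heading of Section 5.0 sets the objective: "Determine the effect of prophylactic dose anticoagulation on markers of thrombin generation during outpatient steady state as well as inpatient VOC".

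For the inpatient part, Section 5.2 (Statistical Analysis) anticipates the numbers and the treatment status: "we expect that 50% of the patients to be hospitalized and continue their medication (placebo or drug) as assigned at randomization". It gives the sampling times, "thrombin generation D-dimer measures will be collected at admission, 3 days and 5 days", and then the comparison, "we will analyze the difference between the placebo and drug groups in the change over time in the mean D-dimer values". Section 5.1 describes the same draws as days 1, 3 and 5, for secondary analysis only, and says of treatment in hospital: "Patients admitted to the hospital will continue their study drug or placebo unless deemed medically inappropriate by admitting physician".

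Three other places bear on the point:

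- The outpatient D-dimer analysis in Section 5.2 runs from enrollment to two months on drug, so its reference value is pre-drug.
- Section 4.2 has in-hospital pain scores compared directly between arms, not as change since admission. It also gives the general model statement (PROC GLM, with the fixed and random effects of the design).
- The closing paragraph of Section 5.2 promises a secondary look at how the arms differ while patients are in hospital. It names no marker, time point or contrast.

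**The concern.** A change-from-baseline contrast measures a treatment effect when the baseline precedes treatment. Here the admission sample is taken from patients who may have been on study drug for weeks or months. A sustained lowering of D-dimer is then in the admission value as well as in the later ones, and differencing removes it. What remains is only the part of the effect that changes between admission and day 5.

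Whether the drug alters the course of D-dimer during a crisis is a fair question, but it is narrower than the Aim 2 objective. A drug that held D-dimer lower throughout the stay could be reported as having no inpatient effect, or as having the less favourable course. The pre-drug enrollment sample that would anchor the comparison is already planned, but this analysis does not use it. The problem does not depend on who is admitted: it would remain if every randomised patient were hospitalised.

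**Working it through.** **Plan's own figure.** No power is stated for the in-hospital analysis. The only D-dimer power in the documents is 0.863, for the outpatient change. It does not follow from the stated design. With 30 per arm, SD 500 and zero correlation, the SD of change is 500 × √2 = 707.1, the SE is 707.1 × √(2/30) = 182.6, and one-sided 0.05 power is Φ(250/182.6 − 1.645) = Φ(−0.276) = 0.39. The value 0.863 returns with 60 per arm and SD 500, or with 60 patients each receiving both treatments: Φ(250/(707.1/√60) − 1.645) = Φ(1.094) = 0.863. That is a separate matter and does not affect the argument below.

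**Inputs from Section 5.2.** Effect 250 (1000 versus 750, or 25%), SD 500, one-sided 0.05, and 50% of 60 patients admitted, so 15 per arm if equal.

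**Assumed, because the documents are silent.** The placebo D-dimer course in hospital; a common within-patient correlation r of 0, 0.5 or 0.8; SD 500 also in hospital; all three draws available. Powers use the normal approximation.

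**What the planned contrast estimates.** Let δ be the drug-minus-placebo difference in mean at a given draw. The difference in change from admission to day 5 is

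C = δ(day 5) − δ(admission).

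The effect at admission cancels. If the effect is constant, C = 0. If the drug mean is 0.75 times the placebo mean P at every draw, C = −0.25 × [P(day 5) − P(admission)], so the sign of C is opposite to the direction of the placebo course.

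**Power of the planned contrast.** SE = 500 × √(2(1 − r)) × √(2/15) = 258.2, 182.6 and 115.5 for r = 0, 0.5 and 0.8. The chance of a result favouring drug is Φ(−C/SE − 1.645). The last column is the average of the admission and day 5 differences.

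| Effect | Assumed placebo course | C | Chance of favourable rejection, r = 0 / 0.5 / 0.8 | Mean level difference |
|---|---|---|---|---|
| Constant −250 | any | 0 | 0.05 / 0.05 / 0.05 | −250 |
| −25% | flat, 1000 | 0 | 0.05 / 0.05 / 0.05 | −250 |
| −25% | 2000 to 1600 | (1200 − 1500) − (1600 − 2000) = +100 | 0.021 / 0.014 / 0.006 | −450 |
| −25% | 2000 to 1000 | +250 | 0.004 / 0.001 / 0.000 | −375 |
| −25% | 2000 to 2500 | −125 | 0.12 / 0.17 / 0.29 | −562.5 |
| −25% | 2000 to 3000 | −250 | 0.25 / 0.39 / 0.70 | −625 |
| Grows from −250 to −500 | any | −250 | 0.25 / 0.39 / 0.70 | −375 |

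In every row the drug arm is lower at both admission and day 5. Where the sign is right, much of the effect is still lost: in the 2000 to 2500 row the contrast keeps 125 of a 562.5 level difference, or 22%.

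**Power of a level comparison (mean of the three draws, true difference 250).**

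- Unadjusted: SE = 500 × √((1 + 2r)/3) × √(2/15) = 105.4, 149.1 and 170.0. Power = Φ(250/SE − 1.645) = 0.77, 0.51 and 0.43.
- Adjusted for enrollment D-dimer, taking its correlation with each inpatient draw as the same r: SE = 500 × √((1 + 2r)/3 − r²) × √(2/15) = 105.4, 117.9 and 86.9. Power = 0.77, 0.68 and 0.89. If enrollment and crisis values correlate less than r, power lies between the unadjusted and adjusted figures.

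**The case against.** A reader might infer that the planned analysis gives a null or wrong-sign result whenever apixaban works. The documents do not support that. They give no in-hospital D-dimer course, and the course decides the sign. If D-dimer rises after admission under a proportional effect, or if the effect grows during the crisis, the contrast points the right way, with power from 0.12 to 0.70 in the cases above.

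A reader might also infer that this is the only inpatient comparison and that a level comparison is ruled out. It is not ruled out. The closing paragraph of Section 5.2 is wide enough to admit one, and a repeated-measures model of the kind described in Section 4.2 would ordinarily yield an arm main effect as well as the arm-by-time term. But neither is named as the inpatient D-dimer test. The fault is a missing specification, and it leaves open a choice between two contrasts that can disagree in sign.

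Nor does the plan postulate a 250 reduction in admitted patients. That figure belongs to the outpatient change from enrollment to two months, and carrying it into hospital is an assumption made here.

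Two further objections stand. Arm-by-time is a legitimate question, so it should be kept. And a within-stay change removes stable differences between patients, which a level comparison does not, except as far as the enrollment value captures them. Admitted patients are selected after randomisation, so the level comparison leans more on the two admitted groups being alike.

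**Conclusion.** The concern holds in limited form. The one in-hospital D-dimer contrast that Section 5.2 names takes an on-treatment value as its baseline and removes whatever effect is present at admission. It can therefore miss or reverse a sustained effect: expectation 0 for a constant effect, wrong sign for a proportional effect with falling D-dimer, and right sign but diluted when D-dimer rises or the effect grows. Which case applies cannot be settled from the documents.

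The cancellation itself is algebra and needs only that patients are on treatment at admission, which Section 5.2 expects. The sizes rest on the assumed courses and correlations, on SD 500 applying in hospital, and on 15 admitted patients per arm.

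The consequence is confined to a secondary analysis in a feasibility study. The primary outpatient D-dimer analysis uses the enrollment value and does not share the problem.

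**What to change.** In Section 5.2, name the between-arm difference in mean in-hospital D-dimer level (admission, day 3 and day 5), adjusted for the pre-drug enrollment D-dimer, as the main inpatient contrast. State how repeat admissions are handled: either the first on-drug admission per patient or a patient random effect. Keep the difference in change over time as a supportive analysis, and show the arm means at each draw so that level and course can be read together. Say that the comparison is exploratory, because admitted patients are a post-randomisation subset.

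The cost is wording only. The enrollment sample and the inpatient draws are already planned, and nothing in patient management changes. The price is the heavier reliance on comparability of the admitted groups, which enrollment adjustment reduces but does not remove.
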